Although the mean data support the effectiveness of BS in the treatment of obesity, the magnitude of WL and the maintenance of weight reduction after BS notably differ among individuals, even among those undergoing the same surgical technique [3]. Data from the pivotal Swedish Obese Subjects (SOS) study show that the maximum WL after BS ranged between -95.5 and + 2.0 kg, and weight regain (WR) after nadir was between 0.0 and 51.4 kg[4]. This heterogeneity in weight trajectory leads some patients to present lower WL than expected and/or the recovery of an important amount of weight after nadir.

At present, it is recognised that the magnitude and maintenance of WL are important to the health results of BS. However, one of the main problems encountered is how to define insufficient WL and pathological WR after BS. A systematic review described that the most frequent definition used for insufficient WL after primary BS is a WL < 50% of the excess weight present prior to surgery with or without a body mass index (BMI) > 35 kg/m² at 18 months after surgery [5]. Thus, insufficient WL is not just the absolute WL but rather the deviation of WL from the result that is usually achieved after BS.

Likewise, in relation to the definition of WR, several studies have used different definitions based on kilograms, units of BMI, or percentage of excess WL regained after nadir or at different time points, including: regain of 10 kg, regain of 25% of excess WL; regain of 15% of initial WL; regain of 5 kg/m²; any WR with a BMI >35 kg/m² at nadir, at 18 months or 3-5 years post-BS [6]. Patients who show WR present a relapse of not only obesity but potentially also the co-morbidities which had remitted during the initial WL. In this case many require revisional surgery or a second procedure to re-achieve WL, either with RYGB, or another procedure such as duodenal switch at the expense of adding a malabsorptive component to the surgical process, which risks extra complications and a high rate of nutritional deficiencies (Annex 1).

The variability of WL or WR has been associated with a wide range of factors related to the surgical technique used, psychological factors, behavioural, dietetic factors, physical activity and comorbidities as well as biological factors which regulate food intake, energy storage and expenditure [7]. Variables such as previous weight, age and the type of surgery explain between 40-50% of the variance in WL, with the rest

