- a) Candidates to primary BS undergoing laparoscopic gastric bypass (LGBP) or laparoscopic sleeve gastrectomy (LSG) from September 2020 to September 2022. This group will be evaluated prior to surgery (a period vulnerable to biases by the request for surgery that affect the answers to the questionnaires for fear of being contraindicated for surgery). The subjects of this group will be followed at 4 months, 1 year, 3 years and 5 years after BS.
- b) A control group of subjects with obesity not candidates to BS matched with the intervention group for age, sex and BMI prior to BS.

*The control group will be recruited by each investigator (10 subjects) and will be evaluated once. According to our casuistic, in order to be comparable with the REGAINSEEN

Versión 2, 07/03/2019

intervention group 80% should be women of 45 years of age with a BMI $> 40 \text{ kg/m}^2$. This group is needed to adjust for variables such as motivation, patient expectations related to surgery and the effect of surgery.

Inclusion criteria:

- Candidate to primary BS from 09/2010 to 09/2021.
- Subjects with obesity ($\geq 40 \text{ kg/m}^2$) not candidates to BS.
- Internet users.
- Primary BS: LGBP and LSG.
- Accept to participate in the study and provide signed informed consent.

Exclusion criteria:

- Second time and/or revisional BS.
- Pregnancy.
- Presence of intellectual impairment impeding the administration of the psychometric tools.
- Type 1 diabetes.
- Dyslexia.

Weight variables: definitions.

- a) The different weight variables will be calculated as follows:
 - Weight lost (kg): Pre-BS weight – weight at nadir.
 - Current weight lost: Pre-BS weight - current weight.
 - Ideal weight: weight corresponding to a BMI = 25 kg/m^2 .
 - Excess weight lost (%): $(\text{Pre-BS weight} - \text{current weight})/\text{excess weight} [(\text{pre-BS weight} - \text{ideal weight}) \times 100]$.
 - Total weight lost (%): $(\text{pre-BS weight} - \text{current weight}/\text{pre-BS weight}) \times 100$.
- b) To study WR the following variables will be calculated:
 - Total WR (%): $(100/(\text{pre-BS weight} - \text{weight at nadir})) * \text{weight regained (kg)}$.
 - Excess WR (EWR %): $[(\text{current weight} - \text{weight at nadir})/\text{excess weight}] \times 100$
 - Weight regained (Kg): current weight – weight at nadir.

Excess weight lost $> 50\%$, total weight lost $> 25\%$ and Excess weight regain $> 15\%$ will be considered as significant.

Psychological evaluation:

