- Social support evaluated by the evaluation protocol using the English Longitudinal Study of Ageing study. APGAR (including 5 questions).
- Quality of life evaluated using the Impact of Weight on the Quality of Life - Lite (IWQOL-lite) questionnaire including 31 questions.

Table 1: Questionnaires on hedonic response to food, addictive behaviour and mood state.

Hedonic response to food	Mood state, stress, negative emotions
DEBQ-external (10)	DEBQ-restraint and emotional (23)
Yale Food Addiction Scale II (25)	Positive and Negative Affect Schedule (PANAS) (20)
Binge eating scale (BITE) (33)	Barrat Impulsivity Scale (30)
Confounding variables	Alcohol Use Disorders Identification Test (AUDIT-4). Fagerström Nicotine Dependence Scale (6)
International Physical Activity Questionnaire (IPAQ) (7).	EPQR-neuroticism (23)
APGAR (5)	Hospital Anxiety and Depression Scale (14)
Quality of life evaluated with the Impact on Weight on the Quality of Life – lite questionnaire (IWQOL-lite) (31)	

Evaluation of food intake: The patients will also complete a registry of foods and drinks consumed over 3 days including a weekend day. It should include the type of food, cooking method, and portion size or weight. Afterwards, the total intake and by macronutrients will be analysed with the Diet Source software (Nestle Health Science. V4.0).

Primary variable:

Body weight: total weight lost (%), excess weight lost (%), total weight regained (%), excess of weight regain (%).

Data collection:

I. Additional information on demographic and anthropometric characteristics and on comorbidities both prior to BS and their evolution over time will be collected in an Excel datasheet designed with this objective and will include the following:

Centre: A number identifying each centre has been assigned starting at 1, with the first 9 numbers having a 0 before them.

REGAINSEEN

Versión 2, 07/03/2019

Code: To register the data of the patients a 5 digit code will identify each patient, with the first 2 numbers corresponding to the number assigned to the centre and the following 3 numbers will correspond to the number assigned to the patient upon entry in the study. For example, the first patient recruited in Hospital Clinic (corresponding to 04) will be assigned the code 001 so that the final code of this patient will be 04001. The code will be kept in each centre and confidentiality will be guaranteed by the investigator.

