The Excel database will not include the number of the clinical history of the patient or any data which could identify the patient.

Study group: 0: control; 1: case

The investigator in each centre should register whether the number of the patient corresponds to a case or a control.

Age: in years

Sex: 0: man; 1 woman

Ethnicity: 0: Caucasian, 1: Gypsy; 2: Latin American; 3: other.

Marital status: 1. Married or with partner; 2. Single; 3. Separated/divorced; 4. Widow.

Lives with (number of people): 1. Alone; 2. Partner/husband/wife; 3. Children, number ...; 4. Parents; 5. Elderly parents/in-laws; 6. other

Occupation: 1. Homemaker; 2. Unskilled worker 3. Skilled worker. 4. Administrative, 5. Contract worker; 6. Retailer; 7. Business person; 8. Other.

Current occupational status: 1. Active/remunerated work; 2. Unemployed; 3. Retired; 4. Temporary work leave; 5. Permanent work leave; 6. Disability.

Level of education: The highest level of education achieved will be registered. 1. No education; 2.- primary; 3. secondary; 4. technical training or similar; 5. university; 6. other.

Comorbidities registered prior to surgery:

➤ Diabetes:

0: normal;

1: altered fasting glucose /intolerance to carbohydrates or previous gestational diabetes;

2: Type 2 diabetes;

3: Type 2 diabetes with HbA1c > 8% 4: insulin treatment.

If a patient classifies as more than one category, this should be separated with a comma. For example, the patient has type 2 diabetes treated with insulin + HbA1c > 8, this would be 2,3,4.

➤ Sleep apnoea

0: normal or Epworth score < 10;

1: Epworth > 10, apnoea-hypopnoea index 5-20;

2: Use of continuous positive airway pressure therapy (CPAP);

3: Cor pulmonale.

➤ Arterial hypertension (AHT):

0 Normotensive (blood pressure (BP) \leq 140/90 mmHg);

1: treatment with 1 hypotensive drug;

2: treatment with more than 2 drugs;

3: decompensated AHT > 140/90 mmHg.

➤ Dyslipidaemia:

0: no;

1: treatment with statins;

2: treatment with fibrates;

3: treatment with statins + fibrates.

➤ High-density lipoprotein (HDL) level \leq 40 mg/dl: 0: no, 1: yes.

➤ Previous cardiovascular events: 0: no; 1: yes .

Psychiatric disorder: 0: no; 1: yes. Add diagnosis.

Variables of weight: Weight in Kg and height in metres at baseline in the two groups; weight at 4, 12, 36 and 60 months in the intervention group and in the control group.

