These data will be used to calculate the absolute WL, % of WL, EWL, BMI lost, the total weight regained (TWR) and the EWR .

Surgery: 0: GBP, 1: LSG

Date of surgery: This will be registered as a date and is in order to adapt the dates of the follow-up visits to the different times.

Follow-up: at 4-6 months, and 1, 3 and 5 years

Diabetes yes/no; diabetes treatment (0: no; 1: metformin, 2: DPP4 inhibition, 3: iSGLT2, 4: Sulfonylureas , 5: GLP-1 analogues, 6: insulin). Likewise, combined treatment

should be separated with a comma. For example, a patient controlled with metformin + iSGLT2 would be 1,3.

AHT yes/no; AHT treatment (0: no; 1: treatment with 1 drug; 2: treatment with > 2 drugs);

Dyslipidaemia: 0: No, 1: Yes; treatment: 0: no, 1: Treatment with statins, 2: treatment with fibrates, 3: treatment with statins + ezetimibe.

Sleep apnoea hypopnoea syndrome (SAHS) yes/no; Use of CPAP yes/no;

Revision surgery: 0: no, 1: yes.

Date of revision surgery: registered in date format.

Analytical parameters: fasting glucose, insulin, HbA1c, creatinine, total cholesterol, HDL.

Bioimpedance: fat mass (FM) %; FM kg; fat free mass: (whatever is available).

Sample size

The study will include 445 patients undergoing BS. It is estimated that the percentage of losses to follow-up at 5 years will not be greater than 10% and thus, at least 400 patients must achieve complete follow-up. This sample size will have a statistical power of 80% for detecting an effect size, that is, differences divided by the standard deviation of at least ≥ 0.281 [11]–[13] in magnitude; this effect size is considered in the literature as being of small magnitude [14], [15], and consequently the statistical power will be greater for greater magnitudes. The study will also be discriminatory for binary variables presenting an association with an odds ratio (OR) of at least ≥ 1.78 [11], [16], [17]. Finally, correlations ≥ 0.6 [18]–[21] will be detected considering that values < 0.5 are not relevant. In the three cases cited the calculations of sample size were made using a bilateral level of significance of 5% and a statistical power of 80%. This sample size will allow adjusting possible confounding factors and generate a multivariate model with a minimum number of covariates (at least 4-7, depending on the final number of events and correlations) to obtain adjusted estimators [22]–[24].

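### No formula or model uses the recorded revision surgery, so a patient who regains weight and is re-operated can be scored as not regained.

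*Combined protocol and SAP*

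**What the plan says.** The primary variable is a set of four: "Body weight: total weight lost (%), excess weight lost (%), total weight regained (%), excess of weight regain" (%). Under Weight variables: definitions, the loss measures start from "Current weight lost: Pre-BS weight - current weight" and the regain measures from "Weight regained (Kg): current weight – weight at nadir". Three thresholds (EWL >50%, TWL >25%, EWR >15%) "will be considered as significant".

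The inputs are listed under Data collection, Variables of weight: "weight at 4, 12, 36 and 60 months in the intervention group and in the control group". The next sentence says what they are for: "These data will be used to calculate the absolute WL, % of WL, EWL, BMI lost, the total weight regained (TWR") and the EWR.

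On re-operation, the Introduction says of patients with regain: "In this case many require revisional surgery or a second procedure to re-achieve WL". The Follow-up items in Data collection include revision surgery (no/yes) and its date. A purpose is given for the date of the primary operation ("Date of surgery: This will be registered as a date and is in order to adapt the dates of the follow-up visits"), but none for the revision date.

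Statistical analysis names logistic regression at a given time, Kaplan-Meier and Cox methods for an event that is not defined, and an MMRM for the course of weight. None of these mentions revision. A SAP is promised before data collection ends. It is to describe the methods in depth, with missing values and multiplicity named as topics.

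**The concern.** Revision done for regain is a consequence of the outcome, and it lowers the weight that defines the outcome. With the formulas as they stand, a post-revision weight can serve as current weight or as a new nadir. Three things follow.

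- **Revised between months 36 and 60.** The patient can be scored as not regained in a month-60 analysis. Regain already seen at month 36 remains in the repeated-measures data.
- **Regain and revision both between months 12 and 36.** No scheduled visit falls in that gap, so the regain may appear in no analysis.
- **EWL% and TWL% after revision.** These values mix the effects of two operations.

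The patients affected are those whose regain led to re-operation, and regain is central to what the study sets out to explain. A missing-data rule would not catch the problem, because a post-revision weight is an observed value.

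**Working it through.** **The plan's own figures.** Sample size states 80% power at two-sided 5% for a standardised difference of 0.281 with 400 completers. The normal formula gives 2 × (1.960 + 0.842)² / 0.281² = 199 per group, 398 in all. Allowing for 10% loss, 400 / 0.90 = 444.4, so 445. For OR 1.78, an assumed lower-group risk of 0.30 to 0.50 needs 191 to 206 per group without continuity correction. These figures stand; the point is a missing rule, not the sample size.

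**One patient through the formulas (all weights assumed).** Height 1.65 m, 117 kg before surgery. Ideal weight = 25 × 1.65² = 68.06 kg; excess = 48.94 kg. Weight is 82 kg at month 12 (nadir), 95 kg at month 36, then revision, and 86 kg at month 60. TWL is taken as (pre − current)/pre × 100.

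| | On 95 kg (before revision) | On 86 kg (after revision) | Threshold |
|---|---|---|---|
| EWL | 22/48.94 = 45.0% | 31/48.94 = 63.3% | >50% |
| TWL | 22/117 = 18.8% | 31/117 = 26.5% | >25% |
| EWR | 13/48.94 = 26.6% | 4/48.94 = 8.2% | >15% |
| TWR | 13/35 = 37.1% | 4/35 = 11.4% | none |

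All three threshold classifications reverse.

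**The same patient revised at month 30, weighing 80 kg at month 36.** The 95 kg never enters the data. EWR is 0% if the nadir updates to 80 kg, and −2/48.94 = −4.1% if it stays at 82 kg. The plan does not say which nadir applies; both score as not regained.

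**Effect on a binary month-60 analysis (all rates assumed).** True regain 30%, predictor present in half, risks 36.0% v 24.0% (OR 1.78). Revising 2, 5 or 10% of patients (9, 22 or 45 of 445) means 7, 17 or 33% of regainers. At 5%, 0.05/0.30 = 16.7% of regainers are revised. If all fall back under 15% EWR, the risks become 30.0% v 20.0%, and the OR is (0.300/0.700)/(0.200/0.800) = 1.71.

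| Patients revised | OR, all fall back | OR, half fall back |
|---|---|---|
| 2% | 1.75 | 1.77 |
| 5% | 1.71 | 1.75 |
| 10% | 1.66 | 1.71 |

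These rows assume that revision is unrelated to the predictor. At 5% revised with all falling back:

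- Regainers with the predictor revised 1.5 times as often: 19.2% v 12.8% of regainers revised, risks 29.1% v 20.9%, OR 1.55.
- The reverse ratio: 13.9% v 20.8% revised, risks 31.0% v 19.0%, OR 1.91 from unrounded risks.

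**Against sampling error.** With 200 per group, the SE of log OR is √(1/72 + 1/128 + 1/48 + 1/152) = 0.22, and the 95% interval around 1.78 is 1.15 to 2.75. The shifts to 1.75, 1.71 and 1.66 are 0.08, 0.18 and 0.31 SE. The shifts to 1.55 and 1.91 are 0.62 and 0.32 SE.

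**Power.** On a slightly different base (lower-group risk 0.30, 200 per group), power is 79% at OR 1.78. If 10% or 20% of regainers in both groups are rescored as not regained, it falls to 72% or 65%.

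**The case against.** **The SAP is still to be written.** It is promised with a full account of methods, and the revision flag and date are already collected, so the main rule can still be set. That stands: nothing is lost yet. But revision is not among the topics named, and the definitions already given, followed literally, produce the mis-scoring.

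**All weights may be what is wanted.** The Objective is association with weight trajectory after surgery. The course of weight regardless of re-operation is a legitimate reading of that for EWL% and TWL%. This also stands, and it is why the fix does not impose a single analysis on the loss variables.

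**Success of the first operation.** A reader might infer that the plan counts a re-operated patient as a success of the first operation. The documents do not support that: they call the thresholds significant, and the study relates eating and psychological variables to weight rather than evaluating the operation.

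**Revisional surgery is excluded.** It is listed with the exclusion criteria, without a statement on timing. Since revision is recorded at follow-up and no rule removes or censors such patients, exclusion at entry is the likelier reading, though it is an inference.

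**Covariate screening could admit revision.** It is not named, and adjusting for a consequence of regain does not correct a mis-scored outcome.

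**The regain may still be seen.** It is, when it is present at month 36 and revision comes later. If regain were the survival event, an event recorded at month 36 would not be undone by a later revision.

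**Conclusion.** The omission is clear from the text. The regain variables use visit weights as they stand, no stated analysis uses the revision fields, and the protocol itself expects many regainers to be re-operated. For the individual patient the effect can be complete, as the worked case shows.

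For the cohort, neither the size nor the direction of the bias is known, because the documents give no revision or regain rate. Under the assumed rates it is probably modest (at most 0.31 SE of the log OR) unless revision is related to the predictor, when it can be larger and go either way. A reader might infer that all regain in revised patients is lost, or that the study's associations are badly biased. The documents support neither: only visits after revision are affected, and regain is hidden throughout only when it and the revision fall between the same two visits. This should be settled in the SAP; it is not a fatal flaw.

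**What to change.** State the following in the promised SAP.

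1. For TWR and EWR, do not use weights after the recorded revision date as current weight or as nadir. Nadir is the lowest pre-revision weight.
2. In the binary regain analysis, and in the survival analysis if regain is its event, count a revision as a regain event from its date if either it is recorded as done for regain, or EWR exceeds 15% on the last available pre-revision weight (the chart weight at revision where there is one). Either criterion is enough. For other revisions, treat later visits as missing or censor at the revision date.
3. Run the MMRM for the weight variables with post-revision values set to missing and again with all observed weights. Name in advance which is main, and report both. For EWL% and TWL% either is defensible; for TWR and EWR, rule 1 points to the first.
4. Report the number revised by predictor level, which shows the likely direction of any bias.

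The chart weight or the reason is needed for revisions between months 12 and 36. In the month-30 example the last visit weight is the month-12 nadir, so EWR on visit weights alone would be 0%.

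The cost is SAP wording plus one or two chart fields for revised patients (9 to 45 of 445 at the assumed 2 to 10%). The reason for revision needs some centre judgement, and one of the two MMRM runs has fewer late weights. A patient revised before month 36 is a regain event in the binary analysis but missing afterwards in that run, which can recover only part of a regain that no visit recorded.

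### Pregnancy is an exclusion criterion but not a follow-up item, so a gestational weight at a scheduled weighing would enter the weight and regain variables unmarked

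*Combined protocol and SAP*

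**What the plan says.** Pregnancy appears as a rule only in the protocol's list of exclusion criteria, with no timing. The one other related entry is a history of gestational diabetes, which is part of a pre-surgery diabetes category.

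The section on weight variables defines regain as "Weight regained (Kg): current weight" minus the nadir weight. This feeds total and excess weight regain, two of the four percentages that form the primary variable, and an excess regain above 15% counts as significant. The two weight-loss percentages also use current weight. No formula has an exception.

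Weights are planned as "weight at 4, 12, 36 and 60 months in the intervention group". The list headed "Follow-up: at 4-6 months, and 1, 3 and 5 years" covers diabetes, hypertension, dyslipidaemia, sleep apnoea, revision surgery with its date, laboratory values and bioimpedance. It does not include pregnancy or delivery.

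On the make-up of the cohort, the control-group note says that to match the "intervention group 80% should be women of 45 years of age with a BMI" above 40.

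**The concern.** The study asks whether eating pattern and psychological variables are associated with weight trajectory. Weight carried because of pregnancy is not the behavioural relapse that regain is meant to capture, yet the formulas treat the two alike. Three things can go wrong at an affected visit:

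- Weight loss is understated.
- Regain is overstated, and the 15% flag may be set falsely.
- If the affected visit would have supplied the nadir, the nadir is recorded too high and later regain is understated.

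The error can fall only on women of childbearing age, so it is tied to age and sex. It could therefore affect the profile attributed to patients who regain. A gestational weight also looks like a valid number, so the plan's missing-data provisions would not pick it up.

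**Working it through.** **The plan's own figure.** The sample size section gives 80% power for a standardised difference of 0.281 at two-sided 5%, with 400 completers of 445 enrolled. An equal split is assumed, since the protocol does not state one. The formula then needs 199 per group, and 200 per group gives 80.2% power. For losses, 400/0.90 = 444.4, rounded up to 445. The figure reproduces and is not in dispute.

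**How much weight sets the flag.** Ideal weight is set at BMI 25, so excess weight = (BMI − 25) × height². At an assumed height of 1.62 m (height² = 2.6244):

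- BMI 40: 0.15 × 15 × 2.6244 = 5.9 kg
- BMI 45: 0.15 × 20 × 2.6244 = 7.9 kg

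Over heights of 1.55-1.65 m the range is 5.4-6.1 kg at BMI 40 and 7.2-8.2 kg at BMI 45.

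**How many women are affected.** From the protocol: 80% women, age 45 and 400 completers, so 0.80 × 400 = 320 women. Assumed, because the documents give no figure:

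- age at surgery is roughly normal with mean 45 and SD 8-12
- 2-6 births per 100 women under 40 per year
- the affected window is 9 months of pregnancy plus 6 months after delivery, i.e. 15/12 = 1.25 years

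Women under 40 at a visit t years after surgery = 320 × Φ((40 − 45 − t)/SD). Affected = that number × birth rate × 1.25, i.e. × 0.025 to × 0.075.

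| Visit | Women under 40 (SD 8 to SD 12) | Affected |
|---|---|---|
| 12 months | 320 × Φ(−0.75) = 73 to 320 × Φ(−0.50) = 99 | 1.8-7.4 |
| 36 months | 320 × Φ(−1.00) = 51 to 320 × Φ(−0.67) = 81 | 1.3-6.1 |
| 60 months | 320 × Φ(−1.25) = 34 to 320 × Φ(−0.83) = 65 | 0.8-4.9 |

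The 12-month row is on the high side. If nobody is pregnant at surgery, only 12 of the 15 months can be filled by then, which gives 73 × 0.02 = 1.5 to 99 × 0.06 = 5.9.

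**Effect on power.** As a separate check, apply an assumed pregnancy rate of 0.2-4% per woman-year to all 320 women. Multiplying by 0.75 year gives 0.5-9.6 women pregnant at a visit, or 0.1-2.4% of 400. Assume that each gains 25 points of excess weight regain and that the SD is 15-20 points. The inflated SD is √(SD² + 25² × f(1 − f)), where f is the affected fraction. At the extreme (f = 0.024, SD 15) it is √(225 + 14.6) = 15.48, and power falls from 80.2% to 77.7%. At 1% per year (f = 0.006) power is 79.6-79.9%.

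**Effect on the binary outcome.** Take the protocol's odds ratio of 1.78 and assume that 50% of patients without regain are exposed. Exposure among true events is then 1.78/2.78 = 0.640. Suppose a fraction of events is false and unrelated to exposure:

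- 2% false: 0.98 × 0.640 + 0.02 × 0.5 = 0.637, odds ratio 1.76
- 5% false: 0.95 × 0.640 + 0.05 × 0.5 = 0.633, odds ratio 1.73

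If exposure differs between younger women and the rest, the shift could differ in size or direction. The documents do not allow that to be calculated.

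**The case against.** The strongest case against is that the problem is small and rests on outside assumptions. Birth rate, age spread, height and gestational gain are all absent from the documents. Age and sex are recorded and can be covariates, which partly adjusts the link. The protocol promises a detailed SAP before data collection ends, where a rule for individual weights could sit. All of this stands as to size. It does not remove the gap, because a later SAP cannot apply a rule to a field that was never collected.

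Several stronger readings are tempting, and the documents do not support them:

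- *That all weight gained in pregnancy over five years is scored as regain.* Only weight carried at a scheduled weighing enters the formulas.
- *That 80% women implies many pregnancies.* The same sentence gives 45 years of age, which makes them infrequent.
- *That 2-9 women are affected at each late visit.* This comes from counting women under 40 at surgery (445 × 0.8 × Φ(−5/SD) = 95-120) and carrying them forward unchanged. By 36 and 60 months they are three and five years older, and the protocol plans on 400 completers.
- *That every affected woman is a false regain event.* Some will not be 6-8 kg above nadir at the visit, and some would have crossed 15% anyway.
- *That the cases can never be found.* Each centre keeps the patient codes, so chart review could recover some. The datasheet alone cannot.
- *That the protocol restricts the exclusion to entry.* It gives no timing, so this is only the natural reading. Even if the exclusion ran throughout follow-up, no field would record a pregnancy.

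**Conclusion.** The gap is real and minor. As written, the plan scores gestational weight at a scheduled visit as ordinary weight in the primary variables, in the 15% flag and possibly in the nadir, and the datasheet holds nothing to mark it. About 2-7 women at 12 months, 1-6 at 36 months and 1-5 at 60 months would be affected under the assumptions shown, and fewer would become false regain events. The overall comparison loses almost no power. The reason to act is that the misclassification is confined to younger women and bears on a binary outcome that classifies individual patients. The missing field can be checked directly in the protocol, but the counts are only as good as the assumed age spread and birth rate.

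**What to change.** Add two columns to the follow-up list in the datasheet: pregnant at this visit (yes/no) and date of last delivery. The protocol already records revision surgery with its date, so this follows its own practice.

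In the SAP, prespecify that weights taken during pregnancy, or within a fixed period after delivery, are set to missing for the weight, regain and nadir variables. The planned mixed model for repeated measurements can use a series with such a gap. The logistic models at a single time point need the SAP's missing-data rule. Report a sensitivity analysis that keeps these weights in.

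The cost is two columns, a short SAP paragraph and one extra analysis. The downside is that a few visit weights drop out of the primary variables. Recording the item prospectively is easier than reconstructing it by chart review across centres.
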